that is sufficient to detect pre-post changes in primary and secondary outcomes rather than spend resources on securing a sample of which half will not be treated. We will also avoid having parents decline to participate due to the chance their teen will not receive the app. We have included two design aspects to control threats to validity¹⁴⁴: (1) we have a 6-week interim measure to create a time-series on the assessment of change; and (2) we will include a measure of communication and knowledge related to influenza as a nonequivalent dependent variable, which we do not expect will change pre to post as a result of the app despite it being subject to the same history, maturation, or regression threats as our primary and secondary measures. We will also include demographics, especially age of the teen and parental age and education, as covariates in the analysis as statistical controls against threats such as maturation.

A description of the app was provided in **Sections 3C.1d** and **3C.4.3c**. Participants will download the app following the procedures outlined in **Section 3C.7.1**. Project staff will provide users with a one-on-one app orientation and how to use its unique features via videoconferencing. Daily notifications will engage users in daily app use and provide up-to-date information on users' progress. Participant responses will also be used to evaluate additional or on-going support of users' needs. To protect privacy and to ensure that the participant is the person completing the app activities, KB will uniquely identify the user's smartphone/tablet based off the device's "hardware footprint". The app will upload all app activity data to the KB secured web server database.

3C.6. Target Population. There are two populations: teens with SCD and their parent. Inclusion criteria for teens are: (a) age 13-17 years; (b) diagnosed with SCD; (c) own a smartphone or tablet, and (d) read and speak English. Parents will be recruited to complete a parent proxy version of the primary outcome measure (child's knowledge acquisition; see **3C.7.2**), but will not use the app. Parent inclusion criteria are: (a) parent/guardian of eligible child and (b) able to speak and read English.

3C.7. Trial Conduct.

3C.7.1. Recruitment and Visit Procedures.

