Data security: KB's server farm has 5 Dell PowerEdge servers with two 3.2 Ghz Xeon processors, four with 32 gigabytes of RAM and one with 64 gigabytes, and three 1 Terabyte hard drives that operate off a hardware RAID5 system, connected to a local area network (LAN) running the Windows 2008 or 2012 operating system and to the Internet through a 20-megabyte Fiber connection. KB programmers monitor and maintain all programs and databases. Sensitive information is protected by a hardware firewall (Cisco ASA 5505) and each server has its own native Windows security software. All KB servers are connected via 1 Gigabit high-speed switched network, ensuring high-speed transfer between machines. All networked computers are protected from viruses by Sunbelt Vipre Enterprise. Nightly backup of each computer protects against data loss.

C.10. Evidence for Scientific Rigor and Potential Limitations. The study has numerous strengths, few limitations, and is scientifically rigorous. The study is theory-driven (i.e., User-centered Design and Social Cognitive theories). Formative data will incorporate multiple stakeholder input. The programming approach will be multi-model and evidence-based (i.e., ADDIE Model, MDA framework, AGILE programming) resulting in a systematic, flexible, and cost-effective approach. Sample sizes are sufficient and supported by the literature. Effectiveness will be evaluated in a within-subjects design which allows for sufficient power (i.e., statistical inference with fewer subjects), efficiency (i.e., quicker trial completion), and longitudinal analysis (i.e., individual changes over time). The study team and environment are strong. Potential limitations are: (1) difficulty recruiting; (2) sources of bias; and (3) lack of control group. We have tried to reduce their impact. We will work closely with the EAB and PAB to maximize recruitment. Our primary outcome measure is new, but we are using a rigorous approach to scale development. Self-report instruments are open to bias, however the use of validated measures are a strength. Limitations of no control group are lessened via the use of a time-series design for outcome changes and use of a nonequivalent dependent variable.

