For Aim 2 (Usability), 14 users are needed to identify any problems that impact $\geq 15\%$ of users at a 90% chance of detection ($\log(1-.90)/\log(1-.15)$). Data on applied formative research suggests that 5 participants is sufficient to identify likes/dislikes and potential errors; thus, the power to detect Level 1 severity usability errors should be more than sufficient with $n=14$.¹⁶⁷ Similar to Phase I, usability outcomes will also include program satisfaction ratings with regards to design, appeal, and functionality. Each concept will be rated on a 5-point Likert scale. Means will be calculated and an average of 67% or higher will be considered acceptable. We will examine mean scores, changes in mean scores, and variation within geographical location. The SUS will serve as the primary criterion for measuring usability.^{113,121,122} Further, we will look for outliers to assess if there may be specific characteristics of users who have or develop problems as the processes evolve.

Effectiveness (AIM 3) is critical to product development and will evaluate whether *Pinpoint* increases communication and pain identification knowledge. Means (standard deviations), medians (interquartile range), distributions, frequencies and percentiles will be used to characterize the primary outcome measure. We will test the within person change over time for knowledge acquisition, SCD disease-specific and transition knowledge, SCD self-efficacy, and family cohesion. Linear regression will assess the effects of age, **biologic sex**, and education. Parents will complete a proxy version of the primary outcome; child and parent-report agreement will be assessed using intra-class correlations and median difference tested using Wilcoxon significance tests. Kolmogorov-Smirnov tests will assess for normal score distribution.

Characteristics of dropouts and/or noncompliant individuals will be examined to shed light on potential weaknesses of the app (differential dropout overall or within certain subgroups). Utilization data will be examined to understand the acceptability and intensity of interactions with the app. The penetration of the app into this at-risk population is very important in understanding potential impact. Complier average causal effect models¹⁶⁸ will be used to examine the intensity of the app's utilization. Mediation models using the latest

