bootstrapping methods^{169,170} will be examined to provide evidence that the changes induced by the treatment effects are consistent with the changes being mediated via the app.

As a sensitivity analysis to demonstrate discordant validity, we will perform the same analysis as on the primary outcome, using the number of correct answers in the CDC Flu IQ (i.e., nonequivalent dependent variable). This outcome should not be impacted by the intervention and we expect to see no change in the mean number correct. Although failure to show a difference is not evidence for no difference, the discordant effect size should provide additional information that the primary results are consistent with an intervention effect.

Evidence for Scientific Rigor and Potential Limitations. The study has numerous strengths, few limitations, and is scientifically rigorous. The study is theory-driven (i.e., User-centered Design and Social Cognitive theories). Formative data will incorporate multiple stakeholder input. The programming approach will be multi-model and evidence-based (i.e., ADDIE Model, MDA framework, AGILE programming) resulting in a systematic, flexible, and cost-effective approach. Sample sizes are sufficient and supported by the literature. Effectiveness will be evaluated in a within-subjects design which allows for sufficient power (i.e., statistical inference with fewer subjects), efficiency (i.e., quicker trial completion), and longitudinal analysis (i.e., individual changes over time). The study team and environment are strong. Potential limitations are: (1) difficulty recruiting; (2) sources of bias; and (3) lack of control group. We have tried to reduce their impact. We will work closely with the EAB and PAB to maximize recruitment. Our primary outcome measure is new, but we are using a rigorous approach to scale development. Self-report instruments are open to bias, however the use of validated measures is a strength. Limitations of no control group are lessened via the use of a time-series design for outcome changes and testing of a nonequivalent dependent variable.

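### The SAP analyses the flu quiz by a separate repeat of the primary analysis and does not define how the two changes will be compared; a within-teen contrast with a confidence interval should be added.

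*Combined protocol and SAP*

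**What the plan says.** Protocol section 3C5.1 gives the reasons for having no control group and then states: "We have included two design aspects to control threats to validity". The two are the 6-week interim measure and the flu quiz. The quiz is included because it is "subject to the same history, maturation, or regression threats as our primary and secondary measures". The section also plans demographic covariates as statistical controls. Section C.10 concludes: "Limitations of no control group are lessened via the use of a time-series design for outcome changes and use of a nonequivalent dependent variable". The SAP repeats that claim almost word for word.

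For the outcomes, the SAP (Analyses) says: "We will test the within person change over time for knowledge acquisition, SCD disease-specific and transition knowledge, SCD self-efficacy, and family cohesion". The exact test is not named. For the flu quiz it says "we will perform the same analysis as on the primary outcome, using the number of correct answers in the CDC Flu IQ", and that "we expect to see no change in the mean number correct". It then adds its own caution, "Although failure to show a difference is not evidence for no difference", and continues that "the discordant effect size should provide additional information that the primary results are consistent with an intervention effect".

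Nowhere do the documents give a formula for the discordant effect size, a measure-by-time term, a confidence interval for the difference between the two changes, or a margin for no change on the flu quiz. Figure 7 schedules both measures for every teen at baseline, week 6 and week 12.

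**The concern.** A measure that shares the primary's threats but not its treatment effect is informative only by comparison: the primary must move more than the flu quiz. Two separate analyses do not show this. A significant change beside a non-significant one is compatible with the same underlying change in both.

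At stake is how far a rise in the primary score can be attributed to the app rather than to retesting, history or maturation. The other design feature helps little here. Section 3C.7.1 places a single assessment before the app is downloaded, so there is no pre-app trend against which to judge the 6- and 12-week scores. Covariates such as age do not remove a mean shift shared by all teens. Much of the argument therefore rests on the flu comparison, and that comparison is left to judgement after the data are seen.

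**Working it through.** **Inputs from the documents.** Evaluable n = 80 (100 less 20%); Bonferroni alpha 0.0167 for three secondary outcomes; family cohesion mean change 6.51, SD 22.8 (all SAP, Sample size). The SAP gives no effect size, alpha or power for the primary or the flu quiz.

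**Assumptions.** Two-sided paired t-tests; alpha 0.05 (0.0167 as a variant); normally distributed changes; correlation r between the primary and flu changes of 0 to 0.3; drift d in units of each measure's SD of change.

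**Step 1: the plan's own figure.** 6.51 / 22.8 = 0.2855. A two-sided paired t-test at 0.0167 needs N = 132 for 80% power and has 54.5% power at n = 80. Then 132 / 0.8 = 165. The SAP states 132, 54% and 165, so its figures reproduce and the same test form is used below.

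**Step 2: equal drift, no app effect, two separate tests.** Let p be the power of one test against drift d. At r = 0 the chance of primary significant and flu not is p(1 − p), which cannot exceed 0.25.
- d = 0.20: p = 0.424; 0.424 × 0.576 = 0.244
- d = 0.25: p = 0.598; 0.598 × 0.402 = 0.240
- d = 0.30: p = 0.755; 0.755 × 0.245 = 0.185
- d = 0.40: p = 0.942; 0.942 × 0.058 = 0.055

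Simulation (100,000 trials per setting) confirms these and adds r = 0.3. The contrast is the mean within-teen difference of the two changes, each divided by its own sample SD; the column shows how often it wrongly favours the primary.

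| Drift in both (SD) | Pattern, r = 0 | Pattern, r = 0.3 | Contrast |
|---|---|---|---|
| 0.10 | 12% | 10% | about 3% |
| 0.20 | 24% | 20% | about 3% |
| 0.25 | 24% | 20% | about 3% |
| 0.30 | 18% | 15% | about 3% |
| 0.40 | 5% | 5% | about 3% |

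With the SAP's own 0.0167 and 0.2855 SD of drift, the pattern appears in 25% (r = 0) and 20% (r = 0.3) of trials, against about 1% for the contrast.

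**Step 3: price of the contrast.** The difference of two standardised changes has SD √(2 − 2r), which is 1.414 at r = 0 and 1.183 at r = 0.3. For a true effect of 0.3 SD without drift, the standardised contrast is 0.3 / 1.414 = 0.212 or 0.3 / 1.183 = 0.254. Power at n = 80 and alpha 0.05 is then 47% or 61%, against 76% for the primary test alone. For an effect of 0.5 SD it is 88% or 96%.

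**Step 4: a real effect plus shared drift.** With an effect of 0.4 SD on top of 0.2 SD drift in both measures, the primary is almost always significant. The pattern then appears when the flu test misses its drift: 1 − 0.424 = 0.576, or 58%. At r = 0.3 the contrast detects the effect in about 84%.

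**Step 5: unequal drift, no app effect.** Ranges are for r = 0 to 0.3.
- Primary 0.3, flu 0.2: contrast wrongly supports the app in 10 to 12%; separate-test pattern 40 to 44%.
- Primary 0.3, flu 0.15: 16 to 21%; pattern 53 to 56%.
- Primary 0.3, flu 0: 47 to 61% (the powers in Step 3); pattern about 0.755 × 0.95 = 72%.

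**The case against.** The strongest reply is that 15 to 25% is the error rate of a rule the SAP does not adopt. The SAP itself warns against treating a null flu result as proof, points to effect size rather than significance, labels the flu analysis a sensitivity analysis and calls the trial's analyses largely descriptive. Under equal drift the two standardised effects are equal in expectation, so a careful comparison of effect sizes would not inherit that rate. This stands: the figure is conditional on a reading the SAP leaves open. What does not stand is that the caveat closes the gap. An effect-size comparison without an estimator or interval leaves the reader to decide what counts as discordant.

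A reader might also infer that the flu quiz is the only substitute for a control group, or that the two changes are never compared. The documents support neither. Section 3C5.1 also names the interim measure and covariates, and the SAP intends an informal comparison.

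A further objection is that the contrast has the right error rate only if both measures drift equally in SD units. Nothing in the documents shows this for a newly built communication and pain measure and a 10-item factual quiz, and dividing by the SD does not make their sensitivities equal. This also stands. It is the reason not to make the contrast the sole test of attribution, although Step 5 shows the separate-test pattern doing worse in each case.

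**Conclusion.** The concern holds as a gap in specification. The SAP gives no formal comparison of primary change with flu change, although the rationale for the flu quiz depends on one and both scores are scheduled for every teen. If support were read from significance beside non-significance, equal drift of 0.2 to 0.3 SD would yield false support in about 15 to 25% of trials with n = 80 and alpha 0.05, against about 3% for a direct contrast. The range rests on assumed drift, two-sided tests and a correlation of 0 to 0.3. It covers the drift sizes where the problem peaks: about 10 to 12% at 0.1 SD and 5% at 0.4 SD.

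It would go too far to call 15 to 25% the trial's false-positive rate, since no decision rule is stated. It would also go too far to say that the contrast settles attribution, since its error rate depends on equal drift. The improvement is worth making because it needs no new data.

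**What to change.** In the SAP's flu paragraph, keep the separate flu analysis and add one prespecified contrast. For each teen, take the baseline-to-12-week change on the primary measure divided by the SD of that change, minus the Flu IQ change divided by its own SD. Report the mean difference with a 95% CI and state that this is the discordant effect size. Present it beside the two separate changes wherever attribution to the app is discussed, without making it the only condition for attribution.

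State two limits with it. First, power is lower than for the primary test alone: at a 0.3 SD effect without drift, about 47% at r = 0 and 61% at r = 0.3, against about 76%. Secondly, the contrast is biased toward the app if the flu quiz drifts less than the primary, for example through insensitivity or a ceiling on its 10 items; the Step 5 figures show the size.

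The cost is a few sentences in the SAP and one additional analysis. No visit, item or participant is added. The text should be fixed before outcome data are examined.
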